## 5.5. Analysis Populations

#### 5.5.1. Safety Population

The safety population will include all subjects who received at least 1 capsule or tablet of study drug. This population will be used for all analyses of accountability, demographics, BCX9930 drug concentrations, and safety. Subjects will be analyzed according to the treatment received.

## 5.5.2. Modified Intent-to-Treat (mITT) Population

The modified intent-to-treat (mITT) population will include all subjects who receive at least 1 capsule or tablet of study drug and have post baseline assessment of PNH symptoms and/or laboratory data. The mITT population will be the population for effectiveness analyses. Subjects will be analyzed according to the treatment intended.

#### 5.5.3. Pharmacokinetic Population

The PK population will include all subjects included in the Safety population for whom a PK concentration was collected. The PK population will be the primary population for the PK listings. Subjects will be analyzed according to the treatment received.

## 5.5.4. Pharmacodynamic Population

The PD population will include all Safety population subjects for whom at least 1 PD or complement biomarker measurement can be obtained. This population will be used for all PD and complement biomarker analyses. Subjects will be analyzed according to the treatment received.

## 5.6. Baseline Definition

For a given subject and assessment, the baseline result generally will be the Day 1 value. For subjects who are directly rolling over from a previous study, the baseline ECG result will be obtained at the subject's final on-treatment visit in the previous study and recorded in the eCRF.

For determination of Hemoglobin (Hb) baseline, only preferred lab values that were not collected within 14 days after the subject received a packed red blood cell (pRBC) or whole blood transfusion will be used. For South African subjects, the local lab will be the preferred lab, and for all other subjects, the central lab will be the preferred lab. All Hb values that meet these criteria and were collected at any time from the preferred lab from the Screening visit up to Day 1 pre-dose will be averaged to determine a baseline value. Values from different labs will not be averaged together. If no preferred lab values are available but there are other lab values that were not collected within 14 days after the subject received any RBC or whole blood transfusion, lab values that meet the criteria will be used in place of the preferred lab values. If there are no baseline lab values that were collected outside the transfusion-

#### CONFIDENTIAL

impacted period, the average of all (central and local labs) pre-treatment values from the Screening visit up to Day 1 pre-dose will be used to determine a baseline value, even if these values are themselves impacted by transfusion. This will lead to a conservative estimate of the baseline as the values could be impacted by transfusion and may be higher than expected as a result.

Derivation of the baseline for the following parameters: reticulocytes, PNH RBC (Type II and III red blood cells), the ratio of PNH RBC to PNH WBC (Type II and III granulocytes), haptoglobin, and FACIT-Fatigue will be as stated for Hb, above.

## 5.7. Derived and Transformed Data

## 5.7.1. Baseline Age

The subject's baseline age will be the age collected on the eCRF at time of consent. If this is missing, baseline age will be calculated as the number of complete years from date of birth through date of informed consent. In the case of a partial date, the lowest age consistent with available information will be used.

## 5.7.2. Study Day

Study Day 1 (or Day 1) is the date of first on-study dose of study drug and values captured on that day will generally be used as the baseline (see Section 5.6) If the date of interest occurs on or after the Study Day 1, then study day will be calculated as (date of interest – Study Day 1) + 1. If the date of interest occurs prior to the date of first dose, then study day will be calculated as (date of interest – Study Day 1) + 1. There is no Study Day 0.

## 5.7.3. Change from Baseline

Change from baseline is calculated as (post-baseline result – baseline result). Percent change from baseline is calculated as (100 x change from baseline/baseline result). If either the baseline or the post-baseline result is missing, the change from baseline and percent change from baseline are set to missing as well. If the baseline result is 0, then the percent change from baseline is set to missing.

## 5.7.4. Fold Change from Baseline

Fold change from baseline (also known as the ratio to baseline) is calculated as (post-baseline result / baseline result). If the baseline result is missing, the fold change is also set to missing.

## 5.7.5. Fold Change from ULN (Fold x ULN)

Fold change from the upper limit of normal (ULN) (also known as the ratio to ULN, fold x ULN, or fold above the ULN) is calculated as (post-baseline result / ULN). If the ULN is missing, the fold x ULN is also set to missing.

#### 5.7.6. Total Time on Dose Level

The total time spent on any dose level will be calculated as the sum of the days on each dose level using the start and stop dates per dose period, including if another dose level was taken in between periods of the particular level in question.

## 5.7.7. End of Study

The end of the study is defined as the date when the last subject completes the last protocol-scheduled visit or terminates early.

## 5.7.8. Treatment-Emergent Adverse Events

An AE is considered treatment-emergent if its start date and time is on or after the date and time of first on-study dose of study drug. If the AE start date is missing and the AE stop date and time is after the start date and time of the first on-study dose of study drug (or the AE is ongoing) then the AE will be considered treatment-emergent. If either or both times are missing, then dates alone will be compared. See Section 5.7.11 for incomplete dates or times.

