13.9.1. Definition of Adverse Events

13.9.1.1. Adverse Event

An AE is any untoward medical occurrence in a clinical study subject. No causal relationship with the study drug/IMP or with the clinical study itself is implied. An AE may be an unfavorable and unintended sign, symptom, syndrome, or illness that develops or worsens during the clinical study. Clinically relevant abnormal results of diagnostic procedures including abnormal laboratory findings (eg, requiring unscheduled diagnostic procedures or treatment measures, or resulting in withdrawal from the study) are considered to be AEs. Abnormal results of diagnostic procedures that are incidental or not clinically relevant are not reportable as AEs.

AEs include the following:

- AEs not previously observed in the subject that emerge during the protocol-specified AE reporting period (see Section 13.9.3).
- Findings from protocol-mandated interventions. This can include laboratory assessments performed in the clinical study. AEs should only be reported if the abnormalities are changes from baseline and are clinically significant as described above.
- Pre-existing medical conditions (other than the condition being studied) judged by the Investigator to have worsened in severity or frequency or changed in character during the protocol-specified AE reporting period.
- In addition, in this study the disease-related events of BTH and thromboembolic events will be reported as AEs, even if deemed related to the disease under investigation.

An adverse reaction is defined in ICH Harmonised Tripartite Guideline E2A as follows: all untoward and unintended responses to a study drug/IMP related to any dose administered. The definition covers also medication errors and uses outside what is foreseen in the protocol, including misuse and abuse of the product. The definition implies a reasonable possibility of a causal relationship between the event and the study drug/IMP. This means that there are facts (evidence) or arguments to suggest a causal relationship.

Surgical procedures should not be reported as AEs. The condition for which the surgery is required should be reported as the AE if it occurs or is detected during the study period. Planned surgical measures permitted by the clinical study protocol and the condition(s) leading to these measures are not AEs if the condition(s) was (were) known before the start of study treatment. In the latter case, the condition should be reported as medical history.

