13.9.2. Recording Adverse Events

AEs spontaneously reported by the subject and/or in response to an open question from the study personnel or revealed by observation will be recorded during the study at the investigational site. Only clinically significant changes from baseline in protocol-mandated assessments such as vital signs, laboratory values, and ECGs should be reported as AEs. Information about AEs and SAEs will be collected from the signing of consent form until the end of the study. The AE term should be reported in standard medical terminology and as a diagnosis (not symptoms) when possible. For each AE, the Investigator will evaluate and report the onset (date and time), resolution (date and time), severity, causality, action taken with study drug, seriousness, and outcome,

Severity will be assessed by the Investigator using the DMID scale.

It is important to distinguish between serious and severe AEs. Severity is a measure of intensity, defined in Section 13.9.1.5, whereas seriousness is defined by the criteria under Section 13.9.1.2. An AE of severe intensity may or may not be considered serious.

Should a pregnancy occur, it must be reported and recorded on BioCryst's pregnancy form. Pregnancy is not regarded as an AE unless there is a suspicion that an investigational product may have interfered with the effectiveness of a contraceptive medication.

The outcome of all pregnancies (spontaneous miscarriage, elective termination, normal birth, or congenital abnormality) must be followed up and documented, even if the subject was discontinued from the study.

All reports of congenital abnormalities/birth defects are SAEs. Spontaneous miscarriages, elective abortions, and still-births should also be reported and handled as SAEs.

13.9.3. Method, Frequency, and Time Period for Detecting Adverse Events and Reporting Serious Adverse Events

Reports of all AEs and SAEs, regardless of Investigator attribution, are to be collected from the time of signing of the informed consent. All AEs and SAEs are to be reported on the AE eCRF.

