## **3.2.** Study Endpoint(s)

#### **3.2.1. Primary Endpoints**

• Measurement of safety and tolerability by subject incidence of graded TEAEs, laboratory abnormalities, changes to vital signs, ECG results, and physical examination findings.

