## 9.2.1. Analysis of Abnormal Laboratory Values

Laboratory abnormalities will be graded according to DMID Adult Toxicity Table (draft version November 2007, see Protocol Appendix 1), with the exception of creatinine clearance and glomerular filtration rate, which will be graded using the National Cancer Institute (NCI) Common Terminology Criteria for Adverse Events (CTCAE) version 4.03.

Any graded abnormality that occurs following the initiation of study drug and represents at least 1-grade increase from the baseline assessment is defined as treatment emergent. The number and percentage of subjects who experience treatment-emergent graded toxicities will be summarized by panel, parameter, time point, and treatment category. Laboratory toxicity shifts from baseline to worst post-baseline grade will be summarized by panel, parameter, toxicity grade, and treatment.

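### The treatment-emergent rule for AEs has no worsening clause, so an AE that starts before the first on-study dose and worsens on drug can be missed if it keeps its original start date

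*SAP*

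**What the plan says.** The primary endpoint (SAP 3.2.1) is: "Measurement of safety and tolerability by subject incidence of graded TEAEs, laboratory abnormalities, changes to vital signs, ECG results, and physical examination findings". The AE part of it depends on one flag, defined in SAP 5.7.8: "An AE is considered treatment-emergent if its start date and time is on or after the date and time of first on-study dose". That section adds a rule for AEs with no start date. They count if they stop after the first on-study dose, "or the AE is ongoing) then the AE will be considered treatment-emergent". Sections 5.7.10 and 5.7.11 complete partial dates and can move a start date to the day of first dose. None of these provisions refers to a change in severity.

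Two other definitions do refer to worsening:

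- Protocol 13.9.1.1 describes an AE as possibly a "sign, symptom, syndrome, or illness that develops or worsens during the clinical study". It also includes pre-existing conditions, other than the disease under study, that are "judged by the Investigator to have worsened in severity or frequency or changed in character during the protocol-specified AE reporting period".
- SAP 9.2.1, matching Protocol 14.3.5, says that a graded laboratory abnormality after the start of study drug that "represents at least 1-grade increase from the baseline assessment is defined as treatment emergent".

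Protocol 13.9.3 says that AEs "are to be collected from the time of signing of the informed consent". Section 13.9.2 asks the investigator to give an onset, a resolution and a severity for each AE.

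**The concern.** Within one primary endpoint, two components treat the same clinical course differently. A laboratory value that is Grade 1 at baseline and reaches Grade 3 on drug is treatment-emergent. An AE that is Grade 1 before the first on-study dose and reaches Grade 3 on drug is not, if it stays in one record with its original start date.

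The flag feeds the overall TEAE summary and, in SAP Table 7, the tables of serious TEAEs, Grade 3 or 4 TEAEs, TEAEs leading to discontinuation or interruption, MAVEs and EOSIs. It also feeds the Kaplan-Meier estimate of time to discontinuation due to a TEAE. In a long-term rollover safety study, an event that was tolerable on entry and became severe with further exposure is one that these tables should show.

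The SAP otherwise leans towards counting. An ongoing AE with no start date is treated as treatment-emergent, and a missing severity is set to the highest (5.7.11). Leaving out worsening runs against that approach.

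**Working it through.** No figure in the plan depends on this definition and no hypothesis is tested (SAP 3.3), so there is no stated number to reproduce. The check applies the rule literally to six types of AE record, with the first on-study dose on Day 1, and then applies it again with a worsening clause added.

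| Record | SAP 5.7.8 as written | With worsening clause |
|---|---|---|
| New AE, starts Day 50 | TEAE | TEAE |
| Starts 10 days before first dose at Grade 1, Grade 3 on Day 40, one record | not a TEAE | TEAE |
| Same course, worsening entered as a new record on Day 40 | TEAE | TEAE |
| Medical-history condition worsens, AE onset Day 40 | TEAE | TEAE |
| Start date missing, AE ongoing | TEAE | TEAE |
| Starts 10 days before first dose, stays Grade 1 | not a TEAE | not a TEAE |

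Only the second type changes. The question is then whether the documents prevent that type from arising.

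**Recording rules.** No passage makes a grade increase a new record. Protocol 13.9.3 has AEs followed to resolution, and has the existing record updated once a diagnosis is made. That is compatible with one record per event, but does not require it. The pre-existing-condition item in 13.9.1.1 does not clearly apply to an event that began after consent, because that event is already an AE in the reporting period.

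**Where such records can arise.**

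1. Between consent and first dose. For subjects off drug for at least 31 days, the baseline visit should fall within 28 days of screening (Protocol Table 4, footnote b). SAP Table 3 has a screening target of Day -35 to -1. Treatment lasts up to 144 × 7 = 1,008 days, and the end-of-study visit comes 21 days after the last dose.
   - With 28 days: 28 / (28 + 1,008 + 21) = 28 / 1,057 = 2.6% of the longest observation period.
   - With 35 days: 35 / (35 + 1,008 + 21) = 35 / 1,064 = 3.3%.
   - Consent may be signed before the first visit (Protocol 11.3), so these are not strict maxima.
   - Direct rollovers consent at the last visit of the parent study, so their window is close to zero.
2. AEs ongoing from the parent study, if they are entered here with their original onset date. Neither document says whether they are.

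**Scale.** The documents give no rate for the affected record type. As a conversion only, each 1% of about 200 subjects holding such a record is 2 subjects. An assumed range of 0% to 10% gives 0 to 20. This counts subjects with such a record. It is not a loss of incidence, because a subject with one missed event may have another TEAE.

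**The case against.** The strongest reply is that the loss is conditional. Under Protocol 13.9.1.1, worsening of a pre-existing condition is itself an AE. Its natural onset is the date of worsening, and SAP 5.7.8 then captures it. The eCRF and its completion guide are not among the documents and may already require a new record. This stands as a limit on the claim, but not as an answer to it: a flag in the primary endpoint should not depend on an unstated convention.

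A second reply is that the documents do not conflict. The protocol definition says what an AE is, and the SAP classifies it by timing. The protocol gives no competing treatment-emergent definition for AEs. That is correct. The point is an omission with a possible wrong count, not a contradiction.

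A third reply is that the events stay visible. Listings 16.2.11.1 to 16.2.11.7 are for all subjects, and their titles are not restricted to treatment-emergent events. Laboratory worsening is counted separately, and ECG parameters and vital signs are summarized as change from baseline. The study has no control group, so no between-arm comparison is biased. All of this stands, and it confines the problem to the AE summary tables.

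A reader might also reason that subjects off drug for at least 31 days will have symptoms before restarting. Those would mainly be PNH symptoms. The disease under study is excluded from the pre-existing-condition item in 13.9.1.1, and PNH symptoms are summarized separately by visit (SAP 8.1.4.4 and 10.1.1). The documents do not support using this to enlarge the count.

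**Conclusion.** The concern holds in conditional form. SAP 5.7.8 has no worsening clause and no recording rule closes the gap. If an AE starts before the first on-study dose, keeps that start date and worsens on drug, the TEAE-based tables omit it while the listings show it. Exposure is limited to AEs starting between consent and first dose, mainly in screened subjects, and to parent-study AEs carried forward with their original onset. The number is probably small, but the documents do not allow an estimate.

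Two stronger readings should be resisted. The first is that worsening AEs simply drop out of the primary endpoint. They do so only if kept as one record, and only from its AE component. The second is a numerical loss. A reader might assume that 10% to 25% of 200 subjects are screened (20 to 50) and that 5% to 10% of those have a worsening pre-dose AE. That gives 20 × 5% = 1 to 50 × 10% = 5 subjects, or 0.5 to 2.5 percentage points. Set against a term seen in 5% of subjects (10), it would look like half the count. Neither rate is in the documents. The sum treats a lost event as a lost subject, and the last step needs all five to share one term and reach the same severity. No percentage-point loss should be claimed.

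**What to change.** Make three changes together:

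1. Add to SAP 5.7.8 that an AE is also treatment-emergent if it started before the first on-study dose and increases in severity grade, or becomes serious, on or after that dose.
2. Instruct sites to record such worsening as a new AE with its own onset date and grade. Without this, the clause may not be programmable, because the protocol does not ask for dated changes in severity within a record. With it, new records are counted by their start date, and the SAP clause settles the status of records already entered.
3. State how AEs ongoing from the parent study are entered, including which onset date is used.

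The cost is a sentence in the SAP, a few lines of site instruction, and queries on existing records with a pre-dose start that were still ongoing at the first on-study dose. The TEAE count may rise slightly. No visit, sample or endpoint changes.

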## 5.7.9. Prior and Concomitant Medications

A medication will be classified as prior if its end date and time are before the date and time of the first onstudy dose of study drug. Otherwise, the medication will be classified as concomitant; that is, its start date and time are on or after the date and time of the first on-study dose of study drug, or its end date and time are on or after the start date and time of the first on-study dose of study drug, or the medication is flagged as ongoing. If either or both times are missing, then dates alone will be compared. See Section 5.7.10 for incomplete dates or times.

## 5.7.10. Missing Start and Stop Dates for Prior and Concomitant Medication

For analysis of medications, a complete date should be established to identify medication as occurring during treatment or not. For the purposes of handling partially reported start and stop dates for medication, the following algorithm will be applied:

• Missing start day, but month and year present:

If study medication had been taken in the same month and year as the occurrence of the medication, then the start day of the medication will be assigned to the day of first dose of study medication.

Otherwise the start day will be set to the first day of the month.

• Missing start day and month, but year present:

If study medication had been taken in the same year as the occurrence of the medication, then the start date of the medication will be assigned to the date of first application of study medication.

Otherwise the start day and month will be set to 01 January.

• Missing end day, but month and year present:

The day will be set to the last day of the month.

• Missing end day and month, but year present:

If the year of trial termination is the same year or prior to the year the medication is reported, the end day and month will be set to the date of trial termination.

Otherwise, the end day and month will be set to 31 December.

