11.3.3. Baseline Visit (Day 1)

For all subjects, Informed Consent and Inclusion/ Exclusion criteria will be reviewed to ensure continued subject eligibility.

Before any study drug is administered the following assessments will be completed:

- Signing of ICF (if no screening visit)
- Review of inclusion and exclusion criteria and prohibited medications
- Review of medical and medication history
- Administration of questionnaires:
 - FACIT fatigue scale
 - QLQ-AA/PNH
 - TSQM
- Subject weight
- Complete physical examination
- Vital signs (BP, temperature, and pulse rate)
- 12-lead ECG
- Blood collection for clinical chemistry, hematology, and coagulation

- Blood sample for PNH clone (RBC and WBC)
- Urine pregnancy test for female subjects of child-bearing potential. A negative urine pregnancy result must be recorded in order for the subject to receive study drug.
- Urine collection for urinalysis with microscopy
- PK blood sample
- PD blood sample
- Review of concomitant medications and AEs
- Disease-specific assessments
 - Assessment of PNH symptoms (fatigue, dyspnea, chest pain/discomfort, difficulty swallowing (esophageal pain), abdominal pain, headache, erectile dysfunction, hemoglobinuria, jaundice)
 - Review of blood transfusions
- Study drug dispensing

Where possible, the questionnaires should be completed by the subject prior to other assessments (except signing of the ICF) to prevent influencing subject perceptions.

11.3.4. On-study Visits (Week 4 and every 4 weeks up to Week 96; Week 96 and every 8 weeks to Week 144)

Subjects will return to the clinic during Week 4 (Study Day 29 ± 3 days) and every 4 weeks up to Week 96 (Study Day $673, \pm 3$ days). Visits should be every 4 weeks until a subject has completed a total of 96 weeks on treatment with BCX9930 (ie, weeks in this study plus weeks in the previous study). Starting at Week 96 (Study Day $673, \pm 3$ days), subjects will return to the clinic every 8 weeks to Week 144 (Study Day $1009, \pm 6$ days).

Subjects do not need to withhold any doses on clinic days or take a dose in the clinic, unless the clinic visit falls during the subject's normal time of dosing.

The following assessments will be performed:

- Administration of questionnaires. Where possible, the questionnaires should be completed by the subject prior to other assessments:
 - FACIT fatigue scale at each visit through Week 96 only
 - TSQM questionnaire at Weeks 12, 24, 48, 72, and 96 only

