#### Study Design:

This is an open-label phase 2 study designed to evaluate the long-term safety of daily oral treatment with BCX9930 in subjects who have participated in a previous BCX9930 trial for PNH and showed a benefit of treatment as determined by the Investigator. The study allows continued access to BCX9930 for enrolled subjects.

Methodology:

Subjects who meet all of the inclusion and none of the exclusion criteria will be enrolled into the study. Study visits will occur at Screening, Baseline/Day 1, Week 4, then every 4 weeks up to Week 96. Once subjects have reached Week 96, subsequent study visits will occur every 8 weeks up to Week 144. Additional visits will be required in the case of rising serum creatinine.

Subjects will receive up to 144 weeks of daily BCX9930.

- For subjects directly rolling over from another BCX9930 study without treatment interruption, no screening visit is required. The final on-study visit assessments in the prior BCX9930 study will serve as the baseline assessments for this study; however, additional relevant baseline assessments for this study may be performed at the final on-treatment visit for the prior study as needed to satisfy enrollment criteria. Enrollment without treatment interruption into the current study will obviate the requirement for a follow-up visit in the previous BCX9930 study.
- Subjects with an interruption of treatment of 1 to 30 days duration will be required to complete a full baseline visit, but no screening visit.
- Subjects with an interruption of treatment of 31 days or greater will be required to complete a full screening visit and then baseline visit.

Prior to Protocol Version 5, the protocol-specified dosing regimen was 500 mg BCX9930 twice daily (BID). Under Protocol Version 5, subjects will receive 400 mg BCX9930 BID.

Safety and tolerability will be evaluated through assessments of TEAEs, laboratory analyses (clinical chemistry, hematology, coagulation and urinalysis), vital signs, ECGs, and physical examination findings. Safety events of special interest, including infections, will be followed.

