#### 5.7.11. Missing Start Date, Stop Date, Severity, or Relationship for Adverse Events

The same conventions to address incomplete dates for prior and concomitant medications will also be used for AEs. Should an event have a missing severity or relationship, it will be classified as having the highest severity and/or strongest relationship to study treatment.

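### The partial-date rule keys on drug taken in the reported year, not on first dose in that year, so a year-only AE onset in a later year is moved to Day 1, by up to about 2.8 years

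*SAP*

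**What the plan says.** SAP 5.7.10 treats two kinds of incomplete start date.

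- **Year only** ("Missing start day and month, but year present"). The test is "If study medication had been taken in the same year as the occurrence of the medication". If it is met, "then the start date of the medication will be assigned to the date of first application of study medication". If not, "Otherwise the start day and month will be set to 01 January".
- **Day missing, month and year known.** The test is the same but applies to month and year. If it is met, "then the start day of the medication will be assigned to the day of first dose of study medication"; if not, the first of the month is used.

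SAP 5.7.11 extends this to adverse events: "The same conventions to address incomplete dates for prior and concomitant medications will also be used for AEs". Neither section requires the imputed date to stay in the reported year, or to fall no later than a recorded stop date.

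On exposure, the SAP synopsis states: "Subjects will receive up to 144 weeks of daily BCX9930".

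**The concern.** The usual purpose of such a rule is to settle cases that straddle the first dose. If the reported month or year contains the first dose, the event is assumed to have started at that dose and so counts as treatment-emergent. The SAP's test is wider. It asks whether drug was taken at any time in the period, and under continuous dosing that is true of nearly every on-treatment month and of every calendar year of dosing. In later years the event is already on treatment, so moving it to Day 1 gains nothing and discards a year that is known.

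What is at stake is the timing of events in a study whose primary purpose is long-term safety. SAP 9.1 estimates time to drug-related rash by Kaplan-Meier, and SAP 9.1.1 does the same for first SARS-CoV-2 infection. A late event with a year-only onset would enter these curves as a Day 1 event, with the whole cohort still at risk. SAP 9.1 also derives AE duration as stop minus start, and SAP 9.1.1 summarises infection duration.

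**Working it through.** **Inputs.** The trigger and assigned dates come from SAP 5.7.10 and their extension to AEs from 5.7.11. Treatment lasts 144 weeks (SAP synopsis). The Week 144 visit has a window of ±6 days (Protocol 11.3.4), and the end-of-study visit is 21 ± 3 days after last dose (Protocol 11.3.7). First application is read as first on-study dose, in line with SAP 5.7.2 and 5.7.8. The calendar dates below are illustrative assumptions.

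**1. The plan's own time scale.** SAP Table 3 sets the target day as week × 7 + 1. For Week 144, 144 × 7 + 1 = 1009, which matches Study Day 1009 in Protocol 11.3.4.

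**2. Largest year-only error as written.** The error is the true onset day minus Day 1.

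| Latest onset considered | Error (days) | Years (÷ 365.25) |
|---|---|---|
| Last of 144 × 7 = 1008 treatment days | 1008 − 1 = 1007 | 2.76 |
| Plus 21 days of follow-up | 1007 + 21 = 1028 | 2.81 |
| Plus both visit windows | 1007 + 6 + 24 = 1037 | 2.84 |

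The last two rows also require that drug was taken in the calendar year of the onset.

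**3. One subject.** Assume first dose on 15 Mar 2021.

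- Onset recorded as 2022: 1 Jan 2022 is 292 days after first dose and 31 Dec 2022 is 656 days after. The imputed start is therefore 292 to 656 days too early.
- Onset recorded as 2023: 1 Jan 2023 is 292 + 365 = 657 days after first dose. The last treatment day, 17 Dec 2023, is 1007 days after. The error is 657 to 1007 days.

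**4. Typical size.** Every first-dose date in a four-year calendar cycle was enumerated, assuming full 144-week exposure and onset uniform over treatment. A course touches 3 or 4 calendar years. Among year-only onsets, 82% would be given the wrong year, 64% would be off by more than one year and 28% by more than two. The mean error is 504 days (1.4 years). These are shares of year-only records, not of all AEs.

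**5. Day missing, month known.** Only the day is replaced, so the month and year survive. With the same first dose:

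- Onset Jun 2022, stop 10 Jun 2022: imputed start 15 Jun 2022, five days after the stop.
- Onset Mar 2021 after consent, stop 10 Mar 2021: imputed start 15 Mar 2021, the first-dose date. SAP 5.7.8 then makes the event treatment-emergent although it ended before dosing. The stop-date check in 5.7.8 does not help, because it applies only when the start date is missing.

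**6. After the change.** If the first-dose date is used only when the reported year is the year of first dose, and 01 January of the reported year otherwise, the maximum year-only error is 365 days. The mean under the assumptions of step 4 is about 160 days, and the imputed year always equals the reported year.

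**The case against.** The strongest reply is that little of consequence moves. The primary endpoint is subject incidence of graded TEAEs and other safety findings. An event that truly began after first dose is treatment-emergent whether dated correctly or to Day 1, so for those events TEAE, serious, Grade 3 or 4 and related-event counts are unchanged. That stands. A reader might infer that the primary safety tables are corrupted, and the documents do not support that. The exception is the AE that ended before first dose, and only between consent and Day 1.

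Second, year-only onsets should be rare. Protocol 13.9.2 asks for onset date and time, visits are every 4 and later every 8 weeks, and SAP 5.3 provides for edit checks and data cleaning. This also stands. The documents give no count, so the effect on any Kaplan-Meier curve cannot be quantified and should not be called material.

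Third, a reader might infer that every partial onset date goes to Day 1. The text does not say so: the month rule assigns a day, while the year rule assigns a full date. Nor is the trigger met in every on-study month, since interruptions are allowed (Protocol 10.5.1) and AEs are still collected after the last dose.

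Fourth, wrong or negative durations are not certain. SAP 9.1 needs a start and a stop date to be present and does not say whether an imputed date qualifies.

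Finally, the sponsor may have meant drug *first* taken in that period. That is plausible, but the text does not say it. SAP 5.1 wants outside statisticians to be able to replicate the analyses, and a programmer following the wording would reproduce the error.

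**Conclusion.** The rule as written gives a wrong result for a narrow class of records. A year-only AE onset in a later calendar year of dosing is moved to Day 1, by up to 1007 days (2.8 years) on treatment, or up to 1028 days with 21 days of follow-up. A bound of about two years would fit only a shorter exposure, such as the 746 days reported to date in Protocol 5.4.1 (745 ÷ 365.25 = 2.04 years), not the planned 144 weeks. If first application meant the first dose in the parent study, the error would be larger.

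The day-missing error is confined to the reported month, but it can reverse start and stop and can misclassify an AE that ended before dosing. The results exposed are the Kaplan-Meier times to drug-related rash and first SARS-CoV-2 infection and, conditionally, AE and infection durations. Few records are likely affected, but each year-only error can be large and the repair is cheap, so the wording should be corrected.

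**What to change.** In SAP 5.7.10, change both conditions to: *if the first on-study dose was in the same month and year (or, for year-only dates, in the same year)*. Otherwise use the first day of the reported month or 01 January of the reported year. Add two bounds: an imputed start is never later than a known stop date and, for on-study AEs, never earlier than consent. State in SAP 9.1 whether imputed dates enter the duration calculations.

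A year-only date will still carry an error of up to about 365 days, which is the unavoidable cost of not knowing the month and day. The change needs SAP wording and minor programming, and no new data.
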